4.1.6 Dose modifications

Before initiating a new treatment cycle, the actual health status will be assessed according to [Flow Chart](#) and described in Section [5.2](#). To continue treatment with further cycles, all of the following retreatment criteria must be met:

- No uncontrolled hypertension (according to Exclusion-Criterion #10)
- QTcF ≤ 470 ms (according to Exclusion-Criterion #9)
- Acceptable tolerability (in case of an adverse event at the planned start of a treatment cycle patients may continue therapy only after recovery to a level which would allow further therapy; i.e. CTCAE grade 1 or pre-treatment value or considered not clinically significant)

In case one of the above mentioned criteria is not fulfilled the patient the administration of study drug(s) should be delayed. Any case of a delay in treatment cycle for more than 2 weeks should be communicated to the study team at Boehringer Ingelheim. The investigator in agreement with the BI study team will decide about further treatment of individual patient, based on known risk/benefit of BI 836880 and BI 754091.

In case an administration is delayed due to an AE, the patient should visit the site at least once a week for assessment of safety laboratory and AEs. More frequent visits may be appropriate as assessed by the Investigator.

Administration of trial drugs has to be stopped temporarily in case of a DLT (see Section [4.1.7](#)). Patients may resume the treatment only after recovery from DLT to at least fulfil retreatment criteria. The future dose of BI 836880 must be a tested dose which is one dose level below the dose received by the patient. The dose level for treatment resumption should

be as prescribed in [Table 4.1.6: 1](#). Treatment has to be discontinued in case the DLT is not reversible.

If a patient develops an interstitial lung disease, the treatment has to be discontinued.

Table 4.1.6: 1

Dose reduction recommendations for BI 836880

BI 836880 received dose	BI 836880 reduced dose
720 mg	360 mg
360 mg	120 mg
120 mg	120 mg (no change)

Dose reduction for BI 754091 is not allowed. The dose of BI 754091 may be delayed for a patient for one cycle, plus an additional 3 weeks (i.e. for up to 6 weeks), because of AEs following discussion with the sponsor.

In combination treatment arms, both drugs (BI 836880 and BI 754091) will be stopped, paused, or re-exposed together unless an AE can be attributed to either BI 836880 or BI 754091. Only if a causal relationship to one trial drug can be unequivocally established, the other trial drug may be continued.

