3.3.4.1 Discontinuation of trial treatment

An individual patient will discontinue trial treatment if:

- The patient wants to discontinue trial treatment, without the need to justify the decision.
- The patient has repeatedly shown to be non-compliant with important trial procedures and, in the opinion of both, the investigator and sponsor representative, is not willing or able to adhere to the trial requirements in the future.
- The patient needs to use concomitant medication that interferes with the investigational medicinal product or trial assessments. Refer to Section [4.2.2.1](#) for prohibited concomitant medications.
- The patient can no longer receive trial treatment for medical reasons (such as surgery, adverse events, other diseases, or pregnancy). Refer to Section [4.1.6](#) for AEs that require treatment discontinuation.
- The patient experiences unequivocal PD by RECIST v1.1 and/or iRECIST (iRECIST applies to Part II only). Refer to Section [5.1.1](#) for details.

Even if the trial treatment is discontinued, the patient remains in the trial and, will undergo the procedures for the end of treatment (EoT) visit and follow up as outlined in the [Flow Chart](#) and Section [6.2.3](#).

For all patients the reason for withdrawal from trial treatment (e.g. AEs) must be recorded in the CRF. These data will be included in the trial database and reported.

During the dose finding part, patients withdrawn for a reason other than having a DLT or patients who miss more than one visit during MTD evaluation period may be replaced after discussion in the SMC if the information that needed to be collected during that visit is not available and makes the patient non-evaluable for the PK analyses or safety parameters (including evaluation for DLTs).

Patients who come off trial due to a DLT will not be replaced.

If a patient should become pregnant during the trial, the study treatment must be immediately stopped. The patient will be followed up until delivery or termination of pregnancy (see Section [5.2.9.2.3](#) for information on pregnancy forms). The data of the patient will be collected and reported in the electronic case report form (eCRF) until the last patient's last visit and any events occurring thereafter will be reported in the BI drug safety database.

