4.1.7 Dose limiting toxicities

DLTs will be recorded throughout the trial, and should be reported to the sponsor (AESIs, see Section [5.2.9.1.4](#)) within 24 hours of first knowledge.

Any of the following AEs will be reported as potential DLTs, and will be classified as DLTs following review by the Investigators and the sponsor, unless unequivocally due to underlying malignancy or an extraneous cause.

DLTs observed during the MTD evaluation period will be considered for MTD determination. However, all AEs and SAEs meeting criteria of DLT observed in all treatment cycles will be considered for determining a Recommended Phase 2 Dose (RP2D)

Haematologic toxicities:

- Any Grade 5 toxicity
- Neutropenia Grade 4 lasting for >7 days
- Grade ≥ 3 documented infection with neutropenia
- Febrile neutropenia (absolute neutrophil count $<1.0 \times 10^9$ cells/L and fever $\geq 38.5^\circ\text{C}$ or a sustained temperature of $\geq 38.0^\circ\text{C}$ for more than 1 hour)
- Grade 4 thrombocytopenia, or Grade 3 thrombocytopenia with bleeding
- Thrombocytopenia of any Grade which requires platelet transfusions
- Grade 4 anaemia unexplained by underlying disease
- Anaemia of any Grade which requires blood transfusions

Non-haematological toxicities:

- AST or ALT >3 times ULN and concurrent total bilirubin >2 times ULN without initial findings of cholestasis
- \geq Grade 4 AST or ALT of any duration
- Any \geq Grade 3 non-haematologic toxicity with the following exceptions:
 - Grade 3 irAE that resolves to \leq Grade 1 or to baseline with immunosuppressive therapy within 2 weeks
 - Grade 3 fatigue that persists <7 days
 - Grade 3 rash that resolves to \leq Grade 1 within 2 weeks
 - Grade 3 or 4 elevation in serum amylase and/or lipase that is not associated with clinical or radiographic evidence of pancreatitis
 - Grade 3 electrolyte abnormality that lasts <72 hours, is not clinically complicated, and resolves spontaneously or responds to conventional medical intervention
 - Grade 3 nausea or vomiting that lasts <48 hours, and resolves to \leq Grade 1 either spontaneously or with conventional medical intervention
 - Alopecia
 - Grade 3 asymptomatic endocrine disorders (thyroid, pituitary, and/or adrenal insufficiency) that are sufficiently managed with or without systemic corticosteroid therapy and/or hormone replacement therapy.
 - Grade 3 tumour flare
- Any Grade 4 or 5 AE other than disease progression
- Any Grade 2 pneumonitis of any duration

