If a patient experiences an infusion-related reaction, acetaminophen and/or an antihistamine (e.g., diphenhydramine) and/or corticosteroid or equivalent medication per institutional standard may be administered prior to subsequent infusions at the discretion of the Investigator for secondary prophylaxis of infusion-related reactions. If an infusion-related reaction is Grade 3 or higher in severity at any point during the study, treatment with BI 836880 and/or BI 754091 will be permanently discontinued.

As with any mAb, allergic reactions to study medication administration are possible. Appropriate drugs and medical equipment to treat acute anaphylactic reactions must be immediately available, and trial personnel must be trained to recognize and treat anaphylaxis. The trial site must have immediate access to emergency resuscitation teams and equipment in addition to the ability to admit patients to an intensive care unit if necessary.

The following terms describe those events that are to be considered potential infusion-related AEs. Regardless of grade, these events are considered as AESIs and must be reported to the sponsor within 24 hours of the event:

- Allergic reaction
- Anaphylaxis
- Cytokine-release syndrome
- Serum sickness
- Infusion reactions
- Infusion-like reactions

If the Investigator determines that another event (not on the list) may be a potential infusion related AE, the Investigator may also report that event as an AESI.

Hepatic injury

A potential hepatic injury is defined by the following alterations of hepatic laboratory parameters in patients with normal aminotransferase levels at baseline:

Proprietary confidential information © 2019 Boehringer Ingelheim International GmbH or one or more of its affiliated companies

- an elevation of AST (Aspartate Aminotransferase) and/or ALT (Alanine Aminotransferase) ≥ 3 fold ULN combined with an elevation of total bilirubin ≥ 2 fold ULN measured in the same blood draw sample, or
- aminotransferase (ALT, and/or AST) elevations ≥ 10 fold ULN.

A potential hepatic injury is defined by the following alterations of hepatic laboratory parameters in patients with abnormal aminotransferase levels of $>$ ULN and ≤ 2.5 fold ULN at baseline:

- an elevation of AST and/or ALT ≥ 3 fold the baseline value combined with an elevation of bilirubin ≥ 2 fold the baseline value measured in the same blood draw sample, or
- aminotransferase (ALT, and/or AST) elevations ≥ 10 fold the baseline value.

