 - BI 754091 should be permanently discontinued for any recurrent Grade 3-4 AE, inability to taper steroids to 10 mg or less prednisone or equivalent within 12 weeks, or persistent Grade 2-3 AEs that do not recover to Grade 1 or less within 12 weeks.
- Adrenal insufficiency:
 - BI 754091 should be permanently discontinued for Grade 3-4 adrenal insufficiency or persistent Grade 2 AEs that do not recover to Grade 1 or less within 12 weeks.
- Rash:
 - BI 754091 should be permanently discontinued for Grade 4 rash, any recurrent Grade 3 AE or persistent Grade 2-3 AEs that do not recover to Grade 1 or less within 12 weeks.
- Encephalitis:
 - BI 754091 should be permanently discontinued for any grade encephalitis.
- Infusion reactions:

Signs and symptoms usually develop during or shortly after drug infusion and generally resolve completely within 24 hours of completion of infusion.

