Rationale for change		
In response to the PMDA's review, the first paragraph was updated for clarification. The discontinuation criteria for interstitial lung diseases were also added in response to a PMDA's review comment.

Section to be changed		4.1.7 Dose limiting toxicities
Description of change		
The following exception from a DLT criterion of $\geq G3$ non-haematologic toxicities was removed: o Grade 3 infusion related reaction which can be controlled by appropriate medication according to investigator's decision, and the subsequent infusion will not be delayed for more than two weeks

Rationale for change		
In response to the PMDA's review, BI is going to handle G3 Infusion related reactions regardless of the controllability

Section to be changed	5.3.2 Methods of sample collection
Description of change	After completion of the trial the plasma and urine samples may be used for further methodological investigations, e.g. for stability testing. However, only data related to the analyte and/or its metabolite(s) including anti-drug antibodies (if applicable) will be generated by these additional investigations. The study samples will be discarded after completion of the additional investigations but not later than 5 years upon the final study report has been signed.
Rationale for change	Correction of error

Section to be changed	7.1.2 Statistical design – Part II (BI 836880 and BI 754091 combination dose finding)
Description of change	A sentence in the 12 th paragraph was updated as follows: Since data from 1336-0012 Part 1 and 1336-0011 1336-0012 were not yet available by the time of finalization of the CTP, data as is might be observed in future in these trials will be used as dummy data.
Rationale for change	Correction of error
Section to be changed	7.1.2 Statistical design – Part II (BI 836880 and BI 754091 combination dose finding)
Description of change	The title of tables 7.1.2: 2 and 7.1.2: 3 was updated as follows: Table 7.1.2: 2 Preliminary data Hypothetical data expected from 1381-0001 Table 7.1.2: 3 Preliminary data Hypothetical data expected from 1381-0004
Rationale for change	Clarification
Section to be changed	7.6 Determination of sample size
Description of change	No formal statistical power calculations of sample size were performed. Approximately 9 patients for Part I are expected, And approximately 1512

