	C1	Incorrect trial medication taken	Decision at MQR (e.g., incorrect dose taken, overdose, use of expired medication etc.)	None	Automatic and manual
	C3	Administration not according to protocol	Decision at MQR (e.g. outside of dosing schedule window, unreasonable drug administration time, etc.)	None	Automatic and manual
	C6	Administration of study medication which exceeded the limit of in-use stability	Decision at MQR	None	Automatic and manual
	C5	Retreatment criteria were not met but the patient is treated (Cycle 2~)	Retreatment criteria was not met according to CTP section 4.1.6	None	Manual

	C7	Dose reduction not done even though patient meets the dose reduction criteria.	Dose reduction not done according to CTP section 4.1.7	None	Manual
	C8	Treatment is not discontinued even though patient meets the discontinuation criteria	Treatment is not discontinued according to CTP section 3.3.4.1	None	Manual
D		Concomitant medication			
	D2	Prohibited medication use	Refer to CTP section 4.2.2.1	None	Manual
E		Incorrect procedure			
	E1	Certain deviations from procedures used to measure secondary data	Decision at MQRM (e.g. incorrect usage of sampling tube, store at wrong temperature, etc.)	None	Manual
Z		Missing Data			
	Z1	Important PK time points not taken	Blood sample not taken at important time point (e.g. end of infusion sample not taken, sample at elimination phase not taken, etc.)	None	Automatic
	Z3	Missing critical safety information in cycle 1	Essential safety information not taken	None	Automatic and manual

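### Protocol Sections 4.1.6 and 5.2.9.1.4 conflict on treatment after a reversible Grade 3–4 infusion-related reaction, and neither is given precedence

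*Protocol*

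**What the plan says.** - **Protocol 4.1.7** treats as a DLT any Grade 3 or higher event under the heading "Grade 3 non-haematologic toxicity with the following exceptions". No exception names infusion-related reactions. A separate line covers Grade 4 and 5 events other than disease progression. Classification follows review by the investigators and the sponsor.
- **Protocol 4.1.6** stops trial drug temporarily for a DLT. On what follows it says: "Patients may resume the treatment only after recovery from DLT to at least fulfil retreatment criteria". BI 836880 then resumes according to Table 4.1.6: 1. The section requires discontinuation for a DLT that is not reversible and for interstitial lung disease. It does not mention infusion-related reactions.
- **Protocol 5.2.9.1.4**, within the definitions of adverse events of special interest, says that after an infusion-related reaction of Grade 3 or higher at any time in the study "treatment with BI 836880 and/or BI 754091 will be permanently discontinued".
- **Protocol 3.3.4.1** refers the site to Section 4.1.6 "for AEs that require treatment discontinuation". Flow Chart footnote k also sends the site to 4.1.6 before each new cycle.
- **SAP 6.2, Table 6.2:1**, important deviation C8, is defined as "Treatment is not discontinued according to CTP section 3.3.4.1".

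**The concern.** Two current sections prescribe different actions for the same event: one a temporary stop with possible resumption, the other a permanent stop. The section that a site is told to consult on discontinuation holds the permissive rule. The permanent stop sits among reporting definitions.

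The protocol itself describes infusion-related reactions as potentially severe (Table 1.4.2: 1) and gives them as one reason for the 48-hour hospitalisation after first dosing. At stake is whether a patient who has had such a reaction is re-exposed. Handling that differs between patients would also change which later cycles are observed. Those cycles matter because Sections 4.1.7 and 5.2 use DLTs from all cycles, including a re-run of the Bayesian model, in choosing the RP2D.

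**Working it through.** No arithmetic applies. The check traces one event, a Grade 3 or 4 infusion-related reaction that resolves, through the sections that could govern it.

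| Step | Section | Result for this event |
|---|---|---|
| Is it a DLT? | 4.1.7 | Yes by default; no exception names it |
| What happens to treatment after a DLT? | 4.1.6 | Temporary stop; may resume once recovered and retreatment criteria are met |
| Is there an event-specific rule? | 5.2.9.1.4 | Permanent discontinuation, with no condition on recovery |
| Where is the site sent for discontinuation rules? | 3.3.4.1 | To 4.1.6 |
| Does the infusion section settle it? | 4.1.5 | No; its stop-and-restart rule covers only Grade 2 or lower reactions that are not DLTs |
| Does the irAE appendix settle it? | 10.2 | No; its infusion-reaction entry gives no action on treatment |

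**DLT status.** The absence of an exception is deliberate. As context, the log for Global Amendment 1 records the removal of a Grade 3 infusion-reaction exception, with the reason that "BI is going to handle G3 Infusion related reactions regardless of the controllability". Two qualifications remain. Classification is subject to the investigator and sponsor review. In Part II, Appendix 10.1 lists infusion reactions among the immune-related events, so the Grade 3 irAE exception in 4.1.7 might apply if the reaction resolves within 2 weeks on immunosuppressive therapy. That would not remove the conflict, because the ordinary retreatment criteria in 4.1.6 also allow continuation after recovery.

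**Scope.** The two rules diverge in practice only for reversible Grade 3–4 reactions. For an irreversible DLT, 4.1.6 also discontinues, and Grade 5 is moot.

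**Part II.** The and/or wording in 5.2.9.1.4 does not say which drug stops. The end of 4.1.6 gives a default: both drugs are handled together unless causality is unequivocally established for one. Flow Chart footnote j says both should be discontinued together if necessary. The three statements are not cross-referenced.

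**Detection.** C8 is judged against 3.3.4.1, which points to 4.1.6. No listed check in Table 6.2:1 refers to 5.2.9.1.4.

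**Effect on the primary endpoint.** A reaction classified as a DLT counts once under either rule. If it occurs in cycle 1, Section 4.1.8 makes the patient evaluable whatever happens afterwards. The MTD count is therefore unchanged.

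**The case against.** The strongest reply is that the rules can be read together. Section 4.1.6 is permissive: recovery is a necessary condition for resuming and does not entitle the patient to further dosing. Section 5.2.9.1.4 is specific and mandatory, so it could be taken to override. The discontinuation triggers in 4.1.6 are not stated to be exhaustive, and Appendix 10.2 adds others for BI 754091. This reading is possible, but the documents do not state it. A temporary stop still clashes with a permanent one, and 4.1.6 does single out one specific event, interstitial lung disease, while omitting this one.

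The reply does defeat several stronger readings that a reader might infer:

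- **That two sites could act in opposite ways and both comply fully.** A site that re-exposes breaches 5.2.9.1.4. A site that stops permanently breaches no resumption rule.
- **That a site would never be led to 5.2.9.1.4.** Section 4.1.7 cites it, though for reporting.
- **That re-exposure would go unflagged.** C8 is a manual check, and 3.3.4.1 also covers patients who can no longer be treated because of adverse events. C3 covers administration not according to protocol, and SAP 6.2 allows the table to be supplemented.
- **That recovery, and so resumption, would be usual.** Appendix 10.2 says infusion reactions "generally resolve completely within 24 hours of completion of infusion", but that appendix applies to Part II only and the sentence is not specific to Grade 3 or higher.
- **That Part II has no rule on which drug stops.** The end of 4.1.6 supplies a default; what is missing is consistency with 5.2.9.1.4.
- **That the patient's exposure and PK data are lost.** Data up to the reaction exist under either rule.

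**Conclusion.** The conflict holds for reversible Grade 3–4 infusion-related reactions, in either part and at any cycle. A site could re-expose a patient relying on 4.1.6, contrary to 5.2.9.1.4, and finding this would depend on manual review.

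Its size cannot be put as a number, because the documents give no rate of such reactions. In a trial of approximately 24 patients it may concern few or none. The consequences are for patient safety and for the later-cycle data that inform the RP2D. They do not extend to the MTD count or to cycle 1 evaluability, provided the reaction is classified as a DLT, which is the default but remains subject to the review and the possible Part II exception. It should be corrected; it does not undermine the dose-finding analysis. No view is taken here on which clinical rule is right.

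**What to change.** 1. Reconcile Protocol Sections 4.1.6 and 5.2.9.1.4 so that one instruction applies to infusion-related reactions of Grade 3 or higher. The sponsor's clinical team decides which rule stands.
2. State or cross-reference that instruction in 4.1.6, where Section 3.3.4.1 and Flow Chart footnote k send the site.
3. Make the and/or wording in 5.2.9.1.4 consistent with the Part II rule at the end of 4.1.6 and with Flow Chart footnote j.
4. Have deviation C8 in SAP Table 6.2:1 cite the reconciled rule.

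The cost is a protocol amendment to wording and one SAP table row. No patients, procedures or analyses are added.

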4.1.2 Selection of doses in the trial

4.1.2.1 Selection of dose in Part I

BI 836880 will be tested from a starting dose of 360 mg in every 3 week administration schedule. The dose-finding will be guided by the BLRM, and the final decision will be made by the SMC (see Section [8.7](#))

BI 836880 monotherapy is currently tested in two phase I trials, trial 1336-0001 for every 3 week administration schedule and trial 1336-0006 for weekly administration schedule, both conducted in Europe. Since the RP2D was already defined in trial 1336-0001 and patient convenience, the every 3 week schedule will be used in this trial. The starting dose was selected based on the data obtained in trial 1336-0001.

In trial 1336-0001, 29 patients were treated with BI 836880, at dose levels between 40 mg and 1000 mg. Amongst them 17 patients received BI 836880 at the recommended Phase 2 dose (RP2D) of 720 mg ([Table 4.1.2.1: 1](#)). The majority of these patients were females (62.1%) with a median age of 57 years. The trial included 6 patients with pancreatic cancer, 4 patients with breast cancer, 4 patients with colorectal cancer 3 patients with oesophageal cancer, as well as other cancer types each represented by 1-2 patients.

BI 836880 was well tolerated in this trial with 1 DLT (pulmonary embolism, CTCAE grade 3) reported at the highest tested dose of 1000 mg.

Table 4.1.2.1: 1 Number of evaluable patients and DLTs in trial 1336-0001

Dose level	BI 836880 dose	Number of evaluable patients	Number of DLTs
1	40 mg	2	0
2	120 mg	2	0
3	360 mg	2	0
4	720 mg	17	0
5	1000 mg	5	1
Total	-	28	1

As of August 2018, 47 patients were treated with BI 836880 monotherapy in trial 1336-0001 or 1336-0006.

Exploratory PK and Pd analysis was performed. BI 836880 plasma exposure is dose-proportional over the dose ranges 40-1000 mg based on C_{max} and partial AUCs. The gmean half-life over all dose groups was 197 hours (cycle 1, n=12), 238 hours (cycle 2, n=7), and 343 hours (cycle 4, n=4). The required trough values of 20 mg/L (according to preclinical experiments) could be achieved at dosages starting from 720 mg every 3 weeks.

Proprietary confidential information © 2019 Boehringer Ingelheim International GmbH or one or more of its affiliated companies

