4.1.2.2 Selection of dose in Part II

BI 836880 will be tested from a starting dose of 120 mg in every 3 week administration schedule. The escalating dose of BI 836880 will be administered in combination with the dose of BI 754091 at 240 mg, which is also administered in every 3 week schedule.

The starting dose of BI 836880 may be adapted via protocol amendment based on the most recent safety information from another ongoing trial, 1336-0011. As of 15 Oct 2018, one DLT was reported in the cohort of BI 836880 360 mg and BI 754091 240 mg cohort.

BI 754091 was tested in monotherapy in the dose-escalation part of trials 1381-0001 and 1381-0004, which were conducted in North America and Japan respectively.

In trial 1381-0001, a total of 9 patients received BI 754091 at 3 dose levels (80 mg, 240 mg and 400 mg) in the dose escalation cohorts. There were no DLTs or drug-related SAEs in any cohort. The most common reported AEs were nausea, fatigue, decreased appetite, constipation and arthralgia. Eight additional patients have been treated at dose of 240 mg in the expansion part of this trial. No grade 4, Grade 5 AE or DLT was reported.

The exploratory analysis of biomarker performed in these 9 patients shows 100% PD-1 receptor occupancy in peripheral blood in all on-treatment patient samples compared to baseline throughout one treatment cycle.

Plasma concentration of BI 754091 appears to increase in dose proportional manner (based on AUC_{0-504h} , C_{max} and C_{pre}). Furthermore, the observed BI 754091 PK was compared with model simulated pembrolizumab PK ([R17-2460](#)). Observed BI 754091 PK profiles overlap with those simulated for pembrolizumab at a dose of 200 mg.

The dose of 240 mg of BI 754091 once every 3 weeks was chosen to be further explored in monotherapy trials and is recommended as a starting dose in combination trials.

In trial 1381-0004, a total of 6 Japanese patients received BI 754091 in the dose-finding part at 240 mg dose level, and none of them experienced DLT or drug related SAE.

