4.1.3 Dose-finding scheme

The dose is planned to be tested in cohorts at pre-defined provisional dose levels. The provisional dose levels to be assigned to different cohorts of patients are listed in [Table 4.1.3:](#)

Proprietary confidential information © 2019 Boehringer Ingelheim International GmbH or one or more of its affiliated companies

1 and 4.1.3: 2. Intermediate or lower dose levels may be investigated if agreed in the SMC, depending on the number of DLTs observed in the trial.

In Part II, increasing doses of BI 836880 will be administered in combination with BI 754091 at 240 mg. The dose of BI 754091 may also be titrated based on DLTs and the overall safety profile of the combination.

Table 4.1.3: 1 Example of dose escalation in Part I*

Dose level	Proposed dose of BI 836880	Increment from previous dose
0	360 mg	Starting dose
1	720 mg*	100%

*Actual dose assignments for a cohort will be communicated separately as determined by the SMC. Intermediate dose level(s) may be investigated depending on the latest DLT rate estimate. Dose levels which are higher than the recommended dose in trial 1336-0001 (720 mg) will not be investigated.

Table 4.1.3: 2 Example of dose escalation in Part II*

Dose level	Proposed dose of BI 836880	Proposed dose of BI 754091	Increment from previous dose (BI 836880)
0	120 mg*	240 mg*	Starting dose
1	360 mg*	240 mg*	200%
2-a	500 mg*	240 mg*	39% (from 360 mg)
2-b	720 mg*	240 mg*	100% (from 360 mg)

*Actual dose assignments for a cohort will be communicated separately as determined by the SMC. Intermediate dose level(s) may be investigated depending on the latest DLT rate estimate. Dose levels which are higher than the recommended dose in trial 1336-0011 will not be investigated. For dose level 2, level 2-a or 2-b will be investigated based on the information from trial 1336-0011.

There will be no dose escalations of BI 836880 or BI 754091 in any one patient.

When the last patient in each cohort completes Cycle 1, the SMC will evaluate the available data. The SMC will review all safety data including, but not limited to, DLTs and all CTCAE Version 5 Grade ≥ 2 toxicity data during cycle 1. Updated safety data on other ongoing patients, including data beyond cycle 1, will be discussed as well. Based on that, a decision on the next dose level to be tested will be made.

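### Protocol Section 4.1.6 contradicts itself on the BI 836880 dose for resuming after a DLT at 120 mg, has no table row for 500 mg, and leaves the term tested dose undefined

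*Protocol*

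**What the plan says.** Protocol Section 4.1.6 lets a patient resume after recovery from a DLT and gives two instructions on the dose, one after the other.

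- The text rule: "The future dose of BI 836880 must be a tested dose which is one dose level below the dose received by the patient".
- The table rule, which begins "The dose level for treatment resumption should" and sends the reader to Table 4.1.6: 1. That table is titled "Dose reduction recommendations for BI 836880" and has three rows: 720 to 360 mg, 360 to 120 mg, and a last row in which 120 mg is followed by "120 mg (no change".

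The same section does not allow the BI 754091 dose to be reduced.

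The planned levels are in Section 4.1.3. Part I has 360 and 720 mg (Table 4.1.3: 1). Part II has 120 mg, 360 mg, and then 500 mg (level 2-a) or 720 mg (level 2-b), each with BI 754091 240 mg (Table 4.1.3: 2). The footnote adds: "For dose level 2, level 2-a or 2-b will be investigated based on the information from trial 1336-0011". Both tables are headed as examples, and the SMC may agree intermediate or lower levels.

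The starting doses are confirmed in Section 4.1.2.1 ("BI 836880 will be tested from a starting dose of 360 mg in every 3 week administration schedule") and Section 4.1.2.2 ("BI 836880 will be tested from a starting dose of 120 mg in every 3 week administration schedule").

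SAP Table 6.2:1, code C7, makes a missed dose reduction an important protocol deviation, with this requirement: "Dose reduction not done according to CTP section 4.1.7".

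**The concern.** The instruction applies to patients who have just had a dose-limiting toxicity. If the sentence and the table differ, two sites can each follow the protocol and give different doses after the same event at the same level. At 120/240 the difference is between a lower dose and the identical regimen, because BI 754091 stays fixed.

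The analysis inherits the problem. C7 asks whether a required reduction was missed, and the answer depends on which instruction is taken as the rule. The dose-reduction summaries in SAP Section 7.7 and the tables of AEs leading to dose reduction in SAP Section 7.8.1 also record what sites did under it.

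**Working it through.** There is no stated figure to reproduce. The check sets each planned level beside the level below it and beside Table 4.1.6: 1.

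| Part and dose received | Planned level below | Table 4.1.6: 1 | Result |
|---|---|---|---|
| Part I, 720 mg | 360 mg | 360 mg | agree |
| Part I, 360 mg | none planned | 120 mg | depends on what tested means |
| Part II, 120 mg | none planned | 120 mg | contradiction |
| Part II, 360 mg | 120 mg | 120 mg | agree |
| Part II, 500 mg (2-a) | 360 mg | no row | gap |
| Part II, 720 mg (2-b) | 360 mg | 360 mg | agree, with 2-a and 2-b as alternatives |

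**The 120 mg row.** The term dose level could also refer to trial 1336-0001, whose levels in Table 4.1.2.1: 1 are 40, 120, 360, 720 and 1000 mg. On that ladder the level below 120 mg is 40 mg. On the Part II levels there is none. Neither reading gives 120 mg, so the row conflicts with the sentence on both.

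**The 500 mg level.** Section 7.1.2 lists 500/240 among its four combination levels, so it is a planned dose. The sentence would lead to the level below in Table 4.1.3: 2. The table that is meant to set the resumption dose says nothing. Any other intermediate dose agreed by the SMC would have no row either.

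**Part I, 360 mg.** On the 1336-0001 ladder, 120 mg is one level below 360 mg and was given there (2 evaluable patients, no DLTs). On the planned Part I levels nothing lies below 360 mg, and Part II, which introduces 120 mg, starts only after Part I is complete (Section 3.1). The protocol does not say which trial or part the word tested refers to.

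**SAP C7.** Section 4.1.7 defines what counts as a DLT. It does not say to what dose a patient is reduced; Section 4.1.6 does. Code C5 in the same SAP table cites 4.1.6 for the retreatment criteria, which suggests that the C7 reference is a slip. Correcting it would not settle the 120 mg case: such a patient complies with the table and deviates from the sentence.

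**Effect on the primary analysis.** Resumption follows the DLT, so the patient is already counted as having had one. The MTD rests on cycle 1 DLTs in evaluable patients, and SAP Section 7.4 summarises DLTs in any cycle by initial treatment. Neither depends on the resumption dose.

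**The case against.** The best defence is that the last row is a deliberate exception for the lowest Part II level. That is a plausible intention, but the sentence is worded as an obligation with no exception, while the table is only recommended. The reader has to guess which prevails.

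It can also be said that the practical exposure is limited. Every DLT goes to the sponsor within 24 hours and is reviewed jointly with the investigators (Section 4.1.7). Irreversible DLTs, interstitial lung disease and Grade 3 or higher infusion reactions lead to discontinuation rather than resumption. Levels 2-a and 2-b are alternatives, so 500 mg may never be used. C7 is assessed manually and excludes no patient, and its trigger, a DLT, is indeed defined in Section 4.1.7. All of this stands and limits the size of the problem. None of it removes the contradiction at 120 mg.

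A reader might infer that the Part I step from 360 to 120 mg is a second flat contradiction. The documents do not support that. Section 4.1.2.1 numbers the 1336-0001 doses as dose levels and calls 360 mg one level lower than the RP2D of 720 mg. On that usage the step fits the sentence, and the SMC may in any case add lower levels.

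**Conclusion.** The point holds in limited form: one direct contradiction (120 mg in Part II), one gap that matters only if 500 mg or another intermediate dose is used, and one ambiguity (tested dose, as it bears on 360 mg in Part I). The SAP cross-reference is a separate minor error. The correction should be made because it concerns dosing after a toxicity, but the MTD, the BLRM and the first-cycle DLT counts do not depend on it.

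A reader might also infer, from the prior mean DLT rate of 0.209 at 120/240 in Table 7.1.2: 6, that the conflict is likely to arise in the first Part II cohort. That does not follow. The rate concerns a DLT, not a DLT followed by recovery and resumption. The prior also rests partly on hypothetical data (Tables 7.1.2: 1 and 7.1.2: 4) that are to be replaced. The documents give no basis for a probability that the conflict occurs.

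The conclusion assumes that both the sentence and the table are in force, as they stand in the current Section 4.1.6.

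**What to change.** - Reconcile the sentence in Section 4.1.6, Table 4.1.6: 1 and Tables 4.1.3: 1 and 4.1.3: 2, so that each planned level in each part, including 500 mg, has one unambiguous instruction. Say also how an intermediate dose added by the SMC is handled.
- State whether a tested dose means tested in the same part, in this trial, or in trial 1336-0001 as well.
- In SAP Table 6.2:1, point C7 to Protocol Section 4.1.6.

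Which instruction applies at each level is a clinical decision for the sponsor's clinical team; this review takes no view on it. The cost is a protocol clarification and one corrected SAP cross-reference. No model, prior or sample size changes.
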